Effectiveness of a 6-week Hippotherapy Program in Children With Autism Spectrum Disorder

NCT04772898

11/21/2023

All data collection sessions will take place at the HETRA facility in Gretna, Nebraska. A summarized description of all assessments can be found in Figure 1. Pre- and post-HPOT assessments will take place in a comfortable room located next to the barn at the HETRA facility. The HPOT session will take place within the barn facility.

Standing posture data will be collected pre- and post-HPOT sessions. To collect standing posture data, ground reaction forces (GRF) and moments will be recorded (200 Hz) from a portable force platform (Bertec Corp., Columbus, OH). During quiet stance trials, children will stand with their feet comfortably apart on the force platform. Foot positioning will be marked and used for all subsequent trials. During each trial, children will be asked to stand as still as possible for 20 s with their arms at their sides and facing a bare wall. Children will perform 3-5 trials of standing.

Social play will also be conducted pre- and post-HPOT session. The principal investigator, a student, and caregivers will engage in 10-minute semi-structured play interactions with the child. We will provide board games, building blocks, books, and similar age-appropriate toys depending upon the age of the child. This session will be videotaped for subsequent analysis of targeted social behaviors. At the end of this session, we will also assess the caregiver's perception of the behavior of their child. This survey examines the alertness, emotional reaction, level of interest and attention, comfort level around strangers, level of activity, overall level of communication, and play behavior of the child. The response required from the parents is a three-point scale that assesses/evaluates at *less*, *typical*, or *more/greater* in each behavioral domain. A similar survey will be used to assess therapist's perception of the success of the HPOT session.

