During the HPOT session, the researchers will monitor the heart rate variability of the horse and the rider. Heart rates will be recorded with the Hylofit system (<https://hylofit.com>) worn by the human and horse, respectively. Both horse and rider will wear an electrode strap around the upper thorax. To assess movement coupling between the horse and rider, five tri-axial inertial sensors (OPAL, APDM, Inc, Portland, OR) will be used. The sensors will collect actively synchronized tri-axial accelerometer and gyroscope data at 80 samples per second. One inertial sensor will be placed dorsal at the rider's pelvis, one frontal at the top of the helmet, and one frontal at the top of the sternum. The sensors on the horse will be fixed on the back of the horse on the spine level between T8 and T10 and on the head. Data will be stored on each sensor's internal memory and downloaded following the collection.

Biostatistical Analysis

Specific Aim 1, Hypothesis 1: For the postural sway and social skill measures, as well as the equine stress measures, we will perform a two-way mixed (2x2) ANOVA. We will compare dependent variables between TD children and children with ASD before and after a 6-week HPOT program.

Specific Aim 2, Hypotheses 1, 2: For the coupling measures of heart rate variability and movement, we will perform an independent t-test between the group of children with ASD and the group of TD children at each session. We will also perform a 2x3 mixed way ANOVA to determine how the coupling measures change over time and with intervention.

Specific Aim 3, Hypothesis 1: We will utilize a multivariate regression model to examine the relationship between changes from pre- to post-HPOT session in standing posture, social behavior, and caregiver perception, with the equine temperament and heart rate and movement coupling indices between horse and rider.

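### Aim 3 should add the pre-session value and ASD/TD group to its posture and social-behaviour models, and report the change-score model alongside

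*Combined protocol and SAP*

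**What the plan says.** Under Biostatistical Analysis, Specific Aim 3, Hypothesis 1, the plan reads "We will utilize a multivariate regression model" and gives its purpose as "to examine the relationship between changes from pre- to post-HPOT session in standing posture, social behavior, and caregiver perception". The predictors follow: "with the equine temperament and heart rate and movement coupling indices between horse and rider". No other covariate is named for this aim.

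The data-collection text shows that the starting values will be available. For posture: "Standing posture data will be collected pre- and post-HPOT sessions". For social behaviour: "Social play will also be conducted pre- and post-HPOT session". Coupling is recorded between the two assessments: "During the HPOT session, the researchers will monitor the heart rate variability of the horse and the rider", and "To assess movement coupling between the horse and rider, five tri-axial inertial sensors" will be used.

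Aims 1 and 2 compare children with ASD and typically developing (TD) children on sway, social skills and coupling. Group is therefore recorded, but it does not appear in Aim 3.

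**The concern.** Subtracting the pre value from the post value fixes the slope on the pre value at 1. If the true slope is below 1, the change score still depends negatively on where the child started. That dependence passes to any predictor correlated with the starting value.

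Coupling is observed, not assigned, and it is measured after the pre-session assessment. A restless child may stand and play less well before the ride and also couple less well during it.

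Aim 3 is the only analysis in the documents that links coupling to the children's outcomes. A slope that can be significant with no coupling effect, or that masks a real one, weakens the only evidence on that question.

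The point covers the posture and social-behaviour outcomes. The caregiver survey uses a three-point scale and would need a different model.

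**Working it through.** **Inputs.** The documents give the outcome (change), the predictors and the timing. They give no sample size, alpha, standard deviation or correlation, so there is no planned figure to reproduce. The following are assumptions:
- unit standard deviation before the session, with outcomes scored so that higher is better;
- pre-post slope rho from 0.3 to 0.9;
- correlation r between coupling and the pre value from 0 to 0.5;
- two-sided alpha 0.05;
- 30 independent records in the simulations (20,000 replicates).

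**Step 1. Precision when r = 0.** Residual variance is 2(1 − rho) for change alone and 1 − rho² with the pre value, so the ratio is (1 + rho)/2.

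| rho | ratio | saving |
|---|---|---|
| 0.3 | 0.65 | 35% |
| 0.5 | 0.75 | 25% |
| 0.7 | 0.85 | 15% |
| 0.9 | 0.95 | 5% |

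**Step 2. Precision when r is not 0.** The variance ratio of the coupling slope, adjusted over change score, is [(1 − rho²)/(1 − r²)] / [(1 − rho)²(1 − r²) + (1 − rho²)].
- At r = 0.3 it is 0.74, 0.84, 0.95 and 1.05 for rho 0.3, 0.5, 0.7 and 0.9.
- At r = 0.5 and rho = 0.5 it is (0.75/0.75)/(0.25 × 0.75 + 0.75) = 1/0.9375 = 1.07. It rises to 1.28 at rho = 0.9.

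So the gain shrinks as r rises and can reverse.

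**Step 3. Mechanism A: the pre-ride state affects coupling.** Let Post = rho × Pre + b × Coupling + error. Then Change = (rho − 1) × Pre + b × Coupling + error. Regressing change on coupling alone gives slope b + (rho − 1)r.
- At rho = 0.5 the bias is −0.5 × 0.3 = −0.15, or −0.5 × 0.5 = −0.25.
- With b = 0.4 the expected slope is 0.25 or 0.15.

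| rho = 0.5, 30 records | change score | with pre value |
|---|---|---|
| False positives, r = 0.3 | 12% | 5% |
| False positives, r = 0.5 | 27% | 5% |
| Power, b = 0.4, r = 0.3 | 26% | 59–60% |
| Power, b = 0.4, r = 0.5 | 12–13% | 52–53% |

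At rho = 0.7 the change-score false-positive rates are about 9% and 18%.

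**Step 4. Mechanism B: a stable trait drives pre, post and coupling, with no coupling effect.** The trait cancels in the change score, so that slope is 0. With the pre value as the only covariate, the coupling slope is (r − rho × r)/(1 − r²).
- At rho = 0.5 and r = 0.3 this is 0.15/0.91 = 0.16.
- At rho = 0.5 and r = 0.5 it is 0.25/0.75 = 0.33.

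In simulation the change score rejects about 5% of the time. The adjusted model rejects about 16% and 43%.

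**Step 5. Mechanism B with ASD/TD group as the trait.** Suppose group shifts pre, post and coupling by 1.5 within-group SD, with a within-group pre-post correlation of 0.5.
- Change alone rejects 5%.
- The pre value without group rejects about 15%, with a false slope of about +0.17 per SD of coupling.
- The pre value with group rejects 4–5%, and its slope has roughly 20% less variance than change with group.

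**The case against.** The strongest counter-argument is that the planned analysis may already be the unbiased one. Step 4 shows this for a stable trait, at the same assumed correlations that make the change score look poor in Step 3. The trial has an obvious candidate for such a trait, since Aims 1 and 2 treat diagnosis as a possible source of difference in sway, social skills and coupling. This objection stands. It is why the pre value should not be added without group, and why the change-score model should still be reported.

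A reader might infer that measuring coupling after the pre-session assessment removes the familiar difficulty with baseline adjustment between pre-existing groups, so that the adjusted slope is simply the right one. The documents do not support that. Time order does not exclude a common cause of all three measurements, and the sample contains two pre-existing groups.

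A reader might also infer that the precision loss and the bias occur together at full size. They do not. The 35%, 25% and 15% savings apply where coupling is unrelated to the pre value, and there the bias is zero.

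Change is also a legitimate target for an observational association. That stands, but it does not argue against the covariate: adjusted for the pre value, change and post value give the same coupling slope.

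Finally, every numerical input is assumed, and independence of the records is uncertain because Aim 2 analyses coupling session by session. The sizes are illustrations. The algebra in Steps 1 to 4 does not depend on the number of records.

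**Conclusion.** The point holds in a limited form. As written, Aim 3 names neither the pre-session value nor group, although both are available.

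Omitting the pre value costs precision when coupling is unrelated to it, and biases the slope when the pre-ride state affects coupling. It does no harm to the slope's validity when a stable trait drives everything. In that case, adjusting for the pre value alone does the harm.

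The documents do not settle which mechanism applies, so neither single-covariate choice is safe. Including both the pre value and group removes the bias due to group and keeps most of the precision gain. A stable trait that varies within the groups would remain, and only a comparison with the change-score model can expose it.

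This is a cheap improvement to the plan and does not show that the planned slope is wrong.

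**What to change.** For each posture and social-behaviour outcome in Aim 3, prespecify a model with the post-session value (or the change) as outcome. The covariates are the same session's pre-session value and ASD/TD group, together with equine temperament and the coupling indices.

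As a sensitivity analysis, report the change-score model with the group term and without the pre-session value. State in advance that a firm conclusion about coupling will be drawn only if the two models agree. If they disagree, report both and say that the result depends on whether pre-ride state or a stable trait explains the link between starting value and coupling.

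The cost is two degrees of freedom and one extra model per outcome. All the data are already due to be collected, and no assessment or session changes.
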